4.5 Endpoint Measurement

4.5.1 Tumor Response (mRECIST criteria)

Evaluation of Target Lesions

Complete Response (CR): Disappearance of any intratumoral arterial enhancement in all target lesions

Partial Response (PR): At least 30% decrease in the sum of diameters of viable (enhancement in the arterial phase) target lesions, taking as reference the baseline sum of the diameters of target lesions.

Stable Disease (SD): Any cases that do not qualify for either PR or PD.

Progressive Disease (PD): An increase of at least 20% in the sum of the diameters of viable (enhancing) target lesions, taking as reference the smallest sum of the diameters of viable (enhancing) target lesions recorded since treatment started.

Evaluation of Non-Target Lesions

Complete Response (CR): Disappearance of all non-target lesions and normalization of tumor marker level. All lymph nodes must be non-pathological in size (<10 mm short axis)

Note: If tumor markers are initially above the upper normal limit, they must normalize for a patient to be considered in complete clinical response.

Non-CR/Non-PD: Persistence of one or more non-target lesion(s) and/or maintenance of tumor marker level above the normal limits

Progressive Disease (PD): Appearance of one or more new lesions and/or unequivocal

progression of existing non-target lesions. Unequivocal progression should not normally trump target lesion status. It must be representative of overall disease status change, not a single lesion increase.

4.5.2 Overall Response (mRECIST criteria)

Target Lesions	Non-Target Lesions	New Lesions	Overall Response
CR	CR	No	CR
CR	IR/SD	No	PR
PR	Non-PD	No	PR
SD	Non-PD	Yes or No	SD
PD	Any	Yes or No	PD
Any	PD	Yes	PD
Any	Any		PD

4.5.3 Milan Criteria

1 tumor \leq 5 cm

OR

\leq 3 tumors, each \leq 3 cm

4.5.4 UCSF Criteria

1 tumor \leq 6.5 cm

OR

\leq 3 tumors with largest diameter \leq 4.5 cm and total of all tumor diameters \leq 8 cm

4.5.5 Local Recurrence

Local recurrence will be evaluated in subjects at the six month post procedure follow-up visit. Subjects will continue to be evaluated every three months thereafter by CT/MRI until liver transplantation or death.

4.5.6 Time to Progression

Time to progression will be tracked as a secondary measure based on the standard of care CT/MRI that all subjects will receive every three months as a requirement to remain on the liver transplant waitlist.

4.6 Adverse Event Reporting

A final phone call, as described in Section 3.10, will be the final adverse event data collection step. No adverse event data collection will occur after that phone call for any patient. The phone call will ensure all possible related adverse events have been identified prior to study closure.

At this point, all ongoing adverse events that have been assessed by the PI to be related to the study intervention will be monitored until resolution or until 3 months has passed since the treatment procedure and use of the study device, the Surefire catheter. These include all adverse events labeled as uncertain, possible, or probable in relation to the study device on the adverse event log. Should an adverse event still be ongoing at 3 months post treatment

procedure, the PI will re-assess the adverse event. While it is expected that most ongoing adverse events at 3 months time would no longer be related, the PI will make the final decision on a per patient basis. Should the PI assess the ongoing adverse event to still be related to the study device, the adverse event will be followed until resolution or until deemed unrelated to the study intervention.

Adverse event data entry in the REDCap database will be incomplete but all adverse events will have full documentation and PI assessment in the patient binders. A drafted revision to the REDCap database was underway when the study was closed by the sponsor and this revision had put a halt to data entry of adverse events in the database. No further data entry will occur for the study as of 06/18/2018 per the sponsor. Final adverse event documentation will be kept in patient binders (to include source documentation and PI review and assessment documentation) and a cumulative adverse event log (to include adverse event name, indication for an SAE, grade, and relationship to intervention) for all patients will be filed in the Regulatory binder. An adverse event is defined as any untoward or unfavorable medical occurrence in a human research study participant, including any abnormal sign (for example, abnormal physical exam or laboratory finding), symptom, clinical event, or disease, temporarily associated with the subject's participation in the research, whether or not it is considered related to the subject's participation in the research.

Adverse events encompass clinical, physical and psychological harms.

Adverse events will be graded by a numerical score according to the defined NCI Common Terminology Criteria for Adverse Events (NCI CTCAE) and version number specified in the protocol. Adverse events not specifically defined in the NCI CTCAE will be scored on the Adverse Event log according to the general guidelines provided by the NCI CTCAE and as outlined below:

- Grade 1: Mild
- Grade 2: Moderate
- Grade 3: Severe or medically significant but not immediately life threatening
- Grade 4: Life threatening consequences
- Grade 5: Death related to the adverse event

Serious Adverse Events (SAEs) are those events which meets any of the following criteria:

- Results in death
- Immediately life-threatening
- Results in inpatient hospitalization or prolongation of existing hospitalization
- Results in persistent or significant disability/incapacity
- Results in a congenital anomaly/birth defect
- Based upon appropriate medical judgment, may jeopardize the subject's health and may require medical or surgical intervention to prevent one of the other outcomes listed in this definition.

A subject who dies or may be hospitalized due to the progression of his/her primary cancer will not be reported as a SAE. A planned hospitalization for a pre-existing condition, or a procedure required by this protocol, without serious deterioration in health, is not considered a SAE. However, any SAEs that are a result of DEB-TACE will be reported as a SAE.

Adverse events are reported to the responsible IRB in accordance with institution requirements and procedures.

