3.10 Follow-Up Procedures

As of 06/18/2018, patients already enrolled will only be followed for ongoing, related adverse events. This is outlined further in Section 4.6.

A follow-up phone call visit is being added to assess adverse events. Upon approval of this protocol, currently enrolled patients will be mailed a letter explaining the change in study status (Appendix 6.5) and be contacted via telephone (Appendix 6.6). The study closeout letter will be sent certified with return receipt requested. A copy of the letter sent and mailing receipt will be filed in the patient binder. The phone call will ensure all possible existing adverse events have been captured and provide an opportunity to assess ongoing, related adverse events before study completion. Only patients still being monitored for adverse events during the first six months post initial treatment procedure will receive this phone call. Patients outside of this first 6 month window will not be called as adverse event data collection for new adverse events has already ceased. The phone call will be documented in the communication log in the patient binder.

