5.4 Data Monitoring

A final monitoring visit will be conducted after all related adverse events have resolved. Monitoring will be limited to ensuring proper study closeout documentation is included and all adverse events have been followed until resolution per this protocol. As necessary, requests for clarification or correction will be sent to the investigator. Risk-based monitoring will be conducted throughout the course of this study.

Independent auditors from the sponsor investigator's authorized representative will be allowed by the site investigator to audit previously monitored data. In addition, audits may be conducted at any time by appropriate regulatory authorities and/or IRB.

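### One closing call, timed by amendment approval, cuts new adverse event collection short of the protocol's own six-month window for every patient called

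*Combined protocol and SAP*

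**What the plan says.** **Trigger.** Section 3.10: "Upon approval of this protocol, currently enrolled patients will be mailed a letter explaining the change in study status", followed by contact by telephone. No call is scheduled at month six and none is repeated.

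**Who is called.** "Only patients still being monitored for adverse events during the first six months post initial treatment procedure will receive this phone call". The reason given for leaving out the others shows the protocol's window for new events: "Patients outside of this first 6 month window will not be called as adverse event data collection for new adverse events has already ceased".

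**Purpose.** In 3.10, "The phone call will ensure all possible existing adverse events have been captured". Section 4.6 goes further and says the call will make sure that every possible related event has been identified before the study closes.

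**End of collection.** Section 4.6: "No adverse event data collection will occur after that phone call for any patient".

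**What continues.** The next paragraph of 4.6 keeps ongoing events judged related under follow-up. They "will be monitored until resolution or until 3 months has passed since the treatment procedure", are then re-assessed by the investigator, and are followed further if still judged related. Section 5.4 agrees: "A final monitoring visit will be conducted after all related adverse events have resolved".

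**Definition and endpoints.** An adverse event in 4.6 is counted whether or not it is related, "including any abnormal sign (for example, abnormal physical exam or laboratory finding" included. Section 2.4.4 lists treatment-related toxicity and change in liver function tests as secondary endpoints. Section 4.4 summarises categorical variables by frequencies and percents; it describes no separate toxicity analysis and no allowance for observation time. Section 3.4 stops follow-up visits and data entry on 18 June 2018.

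**The concern.** A patient qualifies for the call because the six-month window is still open, and the call then closes it. The closing date depends on when the amendment was approved, not on when the patient was treated. Patients past six months at that point had their full window; patients called did not. Two groups with different observation times would enter the same toxicity percentage.

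Truncation can only remove new events, so a crude proportion of patients with an event can be lowered by it but not raised. The completeness statement in 4.6 would tell a reader that nothing related is missing, when an event starting after the call but before month six has no route into the data. For laboratory-defined events there is a further gap: an interview does not measure laboratory values, study visits had stopped, and neither 3.10 nor 4.6 names a source for such results up to the call.

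**Working it through.** The plan states no figure here to reproduce. The check is a reading of the passages, then date arithmetic under stated assumptions.

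**Step 1: the passages together.** New events are collected for six months from initial treatment (3.10). The call follows approval and reaches only patients inside that window (3.10). Adverse event data collection ends at the call (4.6). So for each called patient, months observed for new events = months from initial treatment to call, which is less than six. The direction needs no assumption.

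**Step 2: the most recently treated patient.** Assume initial treatment at closure, 18 June 2018. The window would run to 18 December 2018, which is 183 days. Share observed = days from treatment to call / 183.

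**Step 3: average over called patients.** Assume treatment dates spread evenly up to closure and a call L months after it. Time since treatment among those called is then even between L and 6 months, so mean share observed = (L + 6) / 2 / 6.

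**Step 4: loss over the whole cohort.** Assume also that all 50 planned patients (3.3) were treated evenly over 24 months (the two-year study duration in 1.2, taken here as the accrual period). Patients called = 50 × (6 − L)/24. Mean loss per called patient = (6 − L)/2 months. Planned total = 50 × 6 = 300 patient-months.

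| Lag L (months) | Share, patient treated at closure | Mean share, called patients | Patients called | Patient-months lost | Of 300 |
|---|---|---|---|---|---|
| 1 | 30/183 = 16% | 58% | 10.4 | 10.4 × 2.5 = 26.0 | 9% |
| 2 | 61/183 = 33% | 67% | 8.3 | 8.3 × 2 = 16.7 | 6% |
| 3 | 92/183 = 50% | 75% | 6.25 | 6.25 × 1.5 = 9.4 | 3% |
| 4 | 122/183 = 67% | 83% | 4.2 | 4.2 × 1 = 4.2 | 1% |

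The number enrolled cancels out of the last column, which equals (6 − L)² / (2 × 24 × 6). What matters is the accrual period and its evenness: halving the period to 12 months doubles the share, to 25/144 = 17% at one month and 16/144 = 11% at two.

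**Step 5: what the records would hold.** The cumulative log in 4.6 is to contain event name, an SAE indicator, grade and relationship. It lists neither onset date nor last observation date, so observed time could not be read from the log as described.

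**The case against.** The strongest reply is that the call ends detection of new events and known related events are then followed, so 4.6 and 5.4 fit together and only the wording is loose. This largely stands. A reader might infer from the sentence in 4.6 that all adverse event follow-up stops at the call; the next paragraph of 4.6 and Section 5.4 do not support that. The sentence still needs rewording, because read literally it contradicts what follows.

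It can also be said that 3.10 speaks only of existing events and that 4.6 limits its claim to the time before closure. That helps only if the claim is read as covering events that began by the call, and 4.6 does not say so.

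Other stronger readings are tempting but unsupported:

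- *Laboratory events are missed.* The documents do not say this. Section 3.10 presents the call as an addition, 4.6 keeps source documentation and investigator assessment in patient binders, and chart review is not excluded. Only the absence of a named source is established. Nor do they show that a patient who has died or cannot be reached yields nothing, since earlier records remain.
- *Called patients get far less than six months.* This may be true of the most recently treated, but near month six the loss is small, and the deciding dates are not given.
- *One eighth of planned observation is lost.* The formula gives 37.5/300 = 12.5% at L = 0, a call on the day of closure. The amended text already reports closure as past and places the call after its own approval.
- *Toxicity will be reported as complete, with a known bias.* Section 4.4 sets out no toxicity analysis, and 4.6 openly says database entry of adverse events will be incomplete. Section 4.6 also expects most events still ongoing at three months no longer to be related, so later months may add few related events.
- *Patients lose safety cover.* Section 3.1 places safety monitoring within standard practice. What ends is research data collection.

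**Conclusion.** The point holds in a limited form. For every patient called, new-event collection ends before the protocol's six-month window, and the completeness statement in 4.6 cannot be met for a window still open. Crude toxicity percentages would combine full and truncated observation, with any effect on the proportion being downward.

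The size is not determined by the documents. The illustrative loss of about 9% or 6% of planned patient-months, at one or two months' lag, rests on even accrual over 24 months and an assumed approval date. It measures observation time, not events missed, and should not be cited as the trial's actual loss. The matter deserves correction because the endpoint is a stated one and the remedy is cheap; it does not show that the toxicity results are unusable.

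**What to change.** 1. In 4.6, limit the completeness statement to events with onset up to the call.
2. Reword the sentence that ends collection so that it refers to new events, in agreement with the continued follow-up of ongoing related events in 4.6 and 5.4.
3. At the call, review existing standard-of-care records up to that date (laboratory results, admissions, deaths), including for patients who cannot be reached. File the result in the patient binder, so that no database entry has to be reopened.
4. Add each patient's last adverse event observation date, and event onset dates, to the cumulative log. Report treatment-related toxicity with observed follow-up time, for example per patient-month or separately for full and truncated windows.

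Timing each call to the patient's own six-month date would remove the truncation with the same number of calls. It may also delay a closeout the sponsor has already imposed, since 5.4 would permit earlier closure where no related event is ongoing. That choice belongs to the sponsor; items 1 to 4 are worth making if the immediate call is kept.

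The cost is wording in 4.6, a line in 3.10 for the record review, that short review for each patient in the window, and a less favourable statement of completeness.

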2.4.4 Secondary Endpoints

1. Tumor response (mRECIST criteria) at 3 and 6 months as shown by contrast enhanced CT/MRI
2. Successful downstage to Milan criteria or UCSF criteria
3. Time to progression
4. Treatment-related toxicity
5. Change in Liver Functions Tests
6. Change in Quality of life
7. Changes in AFP levels

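### Section 4.6 re-judges relatedness at 3 months only for persistent events already called related, states the expected answer in advance, and leaves open which attribution the toxicity endpoint uses

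*Combined protocol and SAP*

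**What the plan says.** Section 2.4.4 lists "Treatment-related toxicity" as a secondary endpoint, by name only. The statistical analysis plan in 4.4 has no toxicity analysis.

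Section 4.6, as written for closeout, sets this sequence:

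- Scope: "all ongoing adverse events that have been assessed by the PI to be related to the study intervention will be monitored until resolution".
- First time limit, for an event that has not resolved by then: 3 months from the procedure in which the catheter was used.
- What counts as related: "These include all adverse events labeled as uncertain, possible, or probable in relation to the study device on the adverse event log".
- If an event is still ongoing at 3 months after the treatment "procedure, the PI will re-assess the adverse event".
- The expected result: "While it is expected that most ongoing adverse events at 3 months time would no longer be related". The principal investigator decides case by case.
- An event kept as related is followed until it resolves or is later considered unrelated.

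On records, 4.6 says that REDCap entry of adverse events will be incomplete and has stopped. The patient binders hold the source documents and the investigator's assessments. A cumulative log for all patients goes into the regulatory binder, "to include adverse event name, indication for an SAE, grade, and relationship to intervention".

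Section 5.4 places the final monitoring visit after related events have resolved. The visit checks, among other things, that "all adverse events have been followed until resolution per this protocol".

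**The concern.** Two questions are answered with one label. The first is causal: did the treatment or device bring the event about? The second is operational: does a study that is closing still need to follow it? Persistence to 3 months bears on the second question. By itself it is no evidence against causation, and a lasting related event is usually of more interest than a brief one.

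The step is also asymmetric. Only events already judged related and still ongoing at 3 months are re-judged. An event that resolves earlier keeps its label, and the step has no counterpart that moves an event from unrelated to related. The assessor knows the treatment, works without written criteria, and has read in the protocol what the answer will probably be. If the revised label is the one tabulated, the related-event rate can only fall, and the fall comes entirely from the longest-lasting events.

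**Working it through.** The documents give no adverse event rate, no number ongoing at 3 months and no toxicity analysis, so there is no figure of the plan's to reproduce. The check is a reading of the sections against each other, followed by an illustration.

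**1. Who is re-judged (4.6).** Only events labelled uncertain, possible or probable, and only if ongoing at 3 months. The possible outcomes are related (no change) or unrelated (one fewer related event). Any change is therefore downward.

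**2. On what basis (4.6).** None is stated. No alternative cause has to be documented and no second assessor is named. The only guidance is the sentence giving the expected result.

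**3. Which label reaches the endpoint (2.4.4, 4.4, 4.6).** None of these sections says. The re-assessment is written as a rule on length of follow-up, so replacing the label in the endpoint is possible but not instructed.

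**4. Which record would be tabulated (4.6).** REDCap is incomplete. The binders are complete but held patient by patient. The cumulative log is the only complete cross-patient summary described, and its listed fields include one relationship entry. No separate initial and revised attribution is listed, and no onset, resolution or attribution date. The list may not be exhaustive.

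**5. Related to what (4.6).** The text moves between relation to the study device and relation to the study intervention, while the endpoint concerns treatment. An event judged unrelated to the catheter could still be related to the chemoembolization, so a change of device label need not settle the endpoint.

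**6. When follow-up ends (4.6 against 5.4).** Section 4.6 lets follow-up stop when an event is considered unrelated. Section 5.4 has the visit confirm follow-up to resolution, qualified by a reference back to the protocol. The two can be read together, but the wording should be reconciled.

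**7. Size, illustration only.**

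- Patient level, planned n = 50 (3.3): each patient whose only related event is relabelled changes the rate by 1/50 = 2 percentage points. The study closed early (3.4) and the number treated is not given. For n treated patients the step is 1/n, which exceeds 2 points if n is below 50.
- Event level: let f be the share of related events still ongoing at 3 months and s the share of those relabelled. If the revised label is used, the count of related events falls by f × s. If the protocol's expectation that most would be relabelled came true, s would exceed 0.5. For assumed f of 5%, 10% and 20%, the fall would exceed 0.05 × 0.5 = 2.5%, 0.10 × 0.5 = 5% and 0.20 × 0.5 = 10%. The values of f are assumptions; the documents give none.

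**The case against.** The strongest reply is that this is a closeout rule on how long to follow events, not a rule for the endpoint. Revisiting causality as information accrues is legitimate, and counting uncertain events as related at the start leans towards over-attribution. All of that stands, and it limits the point to what the text permits. It does not supply criteria, justify stating the answer in advance, or say which attribution is analysed.

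A reader might also infer several stronger things that the documents do not support:

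- *The original attribution is lost without trace.* The binders keep the investigator's assessments, so it should be recoverable. The gap is in the summary log.
- *Nobody independent looks at these events.* Under 4.8 the data and safety monitoring committee audits, reviews serious and reportable events sent within 5 business days, and receives six-monthly summaries. Section 5.4 adds a monitoring visit and auditors. None of these is described as reviewing changes of attribution, so the exposure is mainly in non-serious events.
- *Related toxicity is cut off at 3 months.* Events still judged related are followed beyond that point, and duration of toxicity is not a listed endpoint.
- *Sections 4.6 and 5.4 flatly contradict each other.* The qualifier in 5.4 can be read as importing the stopping rule of 4.6.
- *The toxicity rate could be halved.* Going from 10/50 = 20% to 5/50 = 10% needs half of all patients with related toxicity to have only related events that last to 3 months and are all relabelled. Nothing in the documents makes that likely or unlikely.

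**Conclusion.** The point holds in a limited form. Section 4.6 contains a leading, criterion-free re-attribution step that acts only on persistent events already judged related, and the plan does not say which attribution defines treatment-related toxicity. A tabulation from the cumulative log could carry the revised label and understate persistent related events, chiefly non-serious ones.

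The downward direction is certain for any change the step makes to that tabulation. It rests on two conditions: that some events are relabelled, and that the revised label is the one counted. Bias in the endpoint is therefore a risk left open by the text, not an established result. Its size cannot be estimated beyond 2 percentage points per affected patient at the planned 50. This is an inexpensive improvement to a secondary safety endpoint and does not touch the primary analyses.

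**What to change.** - Delete the sentence in 4.6 that states the expected result of the 3-month review.
- State that the original attribution is used for the treatment-related toxicity endpoint and for the cumulative log.
- Record the 3-month re-assessment in a separate, dated field, with a documented reason for any change, and keep both entries. Onset and resolution dates in the log would make persistent events visible.
- Say whether attribution refers to the device, the procedure as a whole, or each separately, so that it matches the endpoint.
- Reconcile the wording of 4.6 and 5.4 on when follow-up ends.

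The cost is a few sentences and a few log columns, filled from binders that already hold the assessments. It needs no new patient contact and no change in care. The reported related-event rate may come out slightly higher.
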